7.2.8 Vital Signs

Vital signs will be measured at the time points described in the Schedule of Assessments ([Table 5](#)).

These assessments include body temperature, systolic and diastolic blood pressure readings (mmHg), heart rate (beats per minute [bpm]), and respiratory rate (respirations per minute [rpm]). Vital signs will be measured immediately prior to infusion, 15 ± 5 , 30 ± 10 , and then every 60 ± 15 minutes during infusion and at end of infusion (± 20 min). The actual time of vital sign measurements should be accurately documented. If the infusion is interrupted and/or subsequently restarted, vital signs should be assessed every 60 ± 15 minutes after the first hour.

The frequency or the length of the monitoring period may be adapted if clinically indicated, for example if in the opinion of the investigator the vital sign results, at the time of event onset, are clinically significant. In such a case the patient's vital sign measurements should continue to be recorded until they have returned to normal or pre-infusion levels and an AE recorded. If possible, before vital signs are measured, the patient should be resting for at least 5 minutes. The same position should be used each time vital signs are measured for a given patient, and blood pressure should be measured from the arm contralateral to the site of study drug administration. Body temperature should be measured according to normal hospital practice.

7.2.9 Physical Examination (PE)

7.2.9.1 Full PE

A full PE will be performed by the Investigator or a qualified designee during the screening and at the EOT Visit.

Full PE must be performed according to the best standards of local medical practice but should include at least vital signs and palpable tumour assessments, general appearance, skin, head, eyes, ears, nose, throat including Waldeyer lymphatic structures, lungs, breasts and axillae (if applicable including bi-dimensional measurement of cervical, supraclavicular, axillary and inguinal lymph nodes), cardiovascular system, back and spine, abdomen (if applicable including spleen size below the costal margin), extremities, infusion site, lymph nodes, and neurological examination.

7.2.9.2 Limited PE

Limited PEs may be focused on tumour response assessment (e.g., lymph nodes, liver, spleen) and AEs per investigator discretion will be performed on Day 1 of Cycles 1, 3, 5, 7, 10 and 12. Additionally, a limited PE will be performed on the 30-Day Follow-up Visit.

During the course of the Additional Treatment Phase of the study a limited PE will be performed on Day 1 every 12 weeks \pm 2 weeks.

Symptom-driven full PEs may be performed as clinically indicated at any study visit.

7.2.9.3 Body Weight and Height Measurements

Body height will be measured at Cycle 1 Day 1 only.

Body weight can be measured up to 24 hours prior to MOR00208 administration on Day 1 of each cycle. This baseline weight will be used to calculate the MOR00208 dose during the given cycle provided the weight does not deviate $>\pm 10\%$ from baseline during the course of this cycle. In cases where the patient's body weight changes more than $\pm 10\%$ from baseline, the current weight will be used to calculate the next and subsequent doses of MOR00208. Using actual body weight prior to each MOR00208 infusion is also allowed, if this is preferred by investigators.

Weight measurements should be performed at each visit and the values will need to be entered into the eCRF on the actual day of measurement.

7.2.9.4 B-Symptoms

B-symptoms are defined as any one or more of the disease-related symptoms or signs mentioned in [Appendix E](#).

Assessment of the presence or absence of B-symptoms will be performed at screening and on Day 1 for all cycles, as well as the End of Treatment Visit and at the 30-Day Follow-up Visit.

7.2.10 Electrocardiogram

Standard 12-lead resting ECGs will be obtained at the various time points described in the Schedule of Assessments ([Table 5](#)). ECGs will be recorded after the patient has rested in a supine position for at least 5 minutes. Heart rate, PR, QRS, RR and QT intervals will be determined. All ECGs will be performed and interpreted locally. The investigator will evaluate the clinical significance of each value outside the reference ranges according to the nature and degree of the observed abnormality. Any new abnormal values considered to be clinically significant should be reported as AEs.

If clinically significant abnormalities are observed or artefacts are present that result in an inability to adequately interpret the results, the ECG will be repeated. An average of all intervals measured in all ECG tracings recorded at a given time point may be taken if necessary.

7.2.11 Adverse Event Monitoring

AEs will be assessed at each visit and reported as specified in [Section 8.2](#) of the protocol.

For screening failure patients only SAEs will be recorded in the eCRF.

7.2.12 Monitoring of Second Primary Malignancies

SPMs will be monitored as events of interest and should be included as part of the assessment of AEs throughout the course of the study. Investigators are to report any SPMs as serious AEs, regardless of causal relationship to the study drugs, occurring at any time, for the duration of the study, from Cycle 1, Day 1 up to and including the follow-up period of up to 3 years. Events of

SPM are to be reported using the SAE report form and must be considered an important medical event even if no other serious criteria apply; these events must also be documented in the appropriate page(s) of the eCRF and the patient's source documents.

Documentation on the diagnosis of the SPMs must be provided at the time of reporting as an SAE (e.g., any confirmatory histology or cytology results, X-rays, computed tomography [CT] scans).

7.2.13 Laboratory Assessments

Detailed instructions and amounts of biological samples needed for the respective laboratory measurements will be summarised in the laboratory manual. All samples will be collected as non-fasting samples.

7.2.13.1 Safety and Haematology Laboratory Testing

Clinical laboratory tests will be performed according to [Table 6](#). During the course of the study, local ("emergency") and central laboratories will be used.

Central laboratory results are required for determining patient eligibility for study enrolment and will be used in the primary statistical analysis of the study results. Note: for eligibility confirmation prior to study drug administration at Cycle 1 Day 1, local laboratory results should be used. During the course of the study, all scheduled central laboratory results should be reviewed as soon as possible after Day 1 of each cycle.

During screening, it is permitted to repeat on a **single occasion** the central laboratory assessment of serum chemistry and haematology parameters due to the variability of the parameters and their dependence on multitude of factors (e.g., hydration, muscle mass). This is, provided no safety concerns arise and that such laboratory results might have been caused by a transient, medically plausible event, which resolved spontaneously or as result of a medical intervention in the meantime (e.g., dehydration, vomiting, imaging procedure with a contrast). This procedure and the rationale behind it must be explicitly documented in source data. Such repeated assessment (once only) of the concerned parameters will not be counted as "re-screening" for that patient.

Local ("emergency") laboratory results will be used for treatment or clinically related decisions, or for the immediate safety needs of a study patient. "Emergency laboratory" (local) results should be reviewed as soon as possible after their receipt and before dosing so that the administration of the investigational medicinal product (IMP) may be adjusted or interrupted if necessary.

The signed and interpreted laboratory results (both local and central) will be kept in the patient's source documentation. The laboratory results should be reviewed, dated and signed in a timely manner by the investigator. Any clinically significant discrepancies will be evaluated on a case-by-case basis. All blood samples will be processed and handled according to standard laboratory procedures. The time of blood collection should be documented in the source data.

If an abnormal laboratory value of grade 4 or an abnormal laboratory value judged to be clinically significant that was not present at baseline, is not reported as an AE, then the investigator should clearly document the rationale for not doing so in the source documentation.

Any abnormal laboratory findings (identified either through local or central laboratory analysis) that constitute an AE should be reported as such and should be followed up until the outcome is known. Also, additional diagnostic tests may be indicated to determine a more precise diagnosis of the patient's condition (e.g., ordering a white blood cell (WBC) differential count to help characterise a high or low WBC count, or ordering a determination of red blood cell (RBC) indices to help characterise a low haematocrit).

Central laboratory tests will be performed only until Cycle 24 for each patient, as applicable.

Table 6 Laboratory Evaluations

Evaluation	Analysis
“Emergency laboratory”¹ (EDTA blood and serum sample)	Serum creatinine, haemoglobin, WBCs, WBC differential, platelets, sodium, potassium, AST, ALT, total bilirubin
Haematology (EDTA blood)	WBC with differential count, haematocrit, haemoglobin, mean corpuscular volume, mean corpuscular haemoglobin concentration, platelet count, RBC count, lymphocytes, monocytes, neutrophils, band neutrophils, eosinophils, basophils At screening: will include a peripheral blood smear Erythrocyte sedimentation rate kit from central lab will be used, however, the test as such has to be performed locally at the site.
Serum chemistry (serum sample)	ALT, total albumin, alkaline phosphatase, amylase, AST, bicarbonate, bilirubin (total), urea, total calcium, chloride, creatinine, creatinine kinase, GGT, glucose, LDH, lipase, phosphate, potassium, protein (total), sodium, uric acid, magnesium, β_2 -microglobulin, C-reactive protein
Coagulation parameters (sodium citrate blood)	Activated partial thromboplastin time, prothrombin time, international normalisation ratio, immunoglobulin concentrations (IgG, IgM, IgA)
Serology parameters (serum sample)	Hepatitis B: HbsAg, anti-Hbc and anti-HBs. HBV-DNA if anti-Hbc positive (until Cycle 24), Hepatitis C: HCV antibody (HCV RNA quantification if anti-HCV-positive)
Pregnancy test (serum sample)	β -HCG serum, females of childbearing potential only
Pregnancy test (urine)	β -HCG urine, females of childbearing potential only. The pregnancy test assay should have a minimum sensitivity of 25 IU/mL (urine sticks will be provided centrally, until Cycle 24).
Urinalysis	Appearance, colour, urine bilirubin, glucose, haemoglobin, ketones, pH, protein, specific gravity, urobilinogen. Microscopy will only be performed if clinically indicated
Genotyping	Fc γ RIIa and Fc γ RIIIa polymorphism
CD16 expression on peripheral NK cells (heparinised blood) (exploratory assay)	CD16 expression on NK cells (Flow cytometry)
Immunogenicity (serum sample)	Anti-MOR00208 antibodies

continued

Evaluation	Analysis
Pharmacokinetics (serum sample)	MOR00208
ADCC assessment (heparinised blood) (exploratory assay)	ADCC with peripheral blood mononuclear cells (Flow cytometry)
B-/T-/NK cell counting (heparinised blood) (exploratory assay)	Cell counts (Flow Cytometry)
Analysis of exploratory biomarkers (pathology samples)	For example: CD19, CD20, BCL-2, BCL-6

Abbreviations: ADCC=antibody-dependent cell-mediated cytotoxicity; ALT=alanine transaminase; AST=aspartate aminotransferase; β -HCG=beta-human chorionic gonadotropin; EDTA=thioldenediaminetetraacetic acid; GGT=gamma-glutamyltransferase; anti-HBc=hepatitis B core antibody; anti-HBs=hepatitis B surface antibody; HbsAg=hepatitis B surface antigen; LDH=lactate dehydrogenase; NK=natural killer; RBC=red blood cell; WBC=white blood cells.

¹WBC differential can be automated or manual as per institutional standards. Reticulocytes may be determined only when clinically indicated.

7.2.13.2 Hepatitis Virus Serology

Patients will be examined according to the schedule in [Table 5](#) for viral hepatitis B and C serology. Hepatitis B biomarkers include hepatitis B surface antigen (HbsAg), total anti-hepatitis B core antibody (anti-Hbc) and hepatitis B surface antibody (anti-HBs). Patients with a positive test for anti-Hbc can only be included if hepatitis B viral DNA (HBV DNA) is not detected. **In these patients only**, HBV DNA should be assessed at various subsequent visits as outlined in [Table 5](#). Note: Central laboratory tests will need to be performed only until Cycle 24 for each patient, as applicable.

In the context of exclusion criteria, seropositive for or active viral infection with hepatitis B virus (HBV) means:

- a) HBV surface antigen positive
- b) HBV surface antigen negative, HBV surface antibody positive and/or HBV core antibody positive and detectable viral DNA. Note: Subjects who are HBV surface antigen negative and viral DNA negative are eligible.
- c) Patients who exhibit the classical vaccination profile of HBV surface antibody positive, HBV core antibody negative, and HBV surface antigen negative are eligible.

If HBV-DNA becomes detectable during treatment, patients should be prophylactically treated and followed-up for potential hepatitis B reactivation as per local medical practice or institutional guidelines for CD20 antibodies such as RTX. If the HBV-DNA assay is positive, then patients can only stay in the study if they are assessed by a physician experienced in the treatment of

hepatitis B and pre-emptive treatment is initiated, if deemed appropriate, and/or according to local practice/guidelines.

Hepatitis C serology is to be done at screening only. Hepatitis C biomarkers include anti-hepatitis C virus antibody (anti-HCV). For patients who are positive for anti-HCV antibody, HCV-RNA should be measured

A positive Hepatitis C test is defined as a positive test for Hepatitis C Virus (HCV) antibodies **and** a positive test for HCV RNA.

7.2.13.3 Pregnancy Testing

A pregnancy test will be performed for females of childbearing potential (FCBP) at various pre- and post-treatment time points either by urine pregnancy test or beta-human chorionic gonadotropin (β -HCG) test of a serum sample (see [Table 5](#)). The pregnancy test assay should have a minimum sensitivity of 25 IU/mL. At screening and the End of Treatment Visit, a serum β -HCG pregnancy test should be performed for FCBP.

FCBP must have two negative pregnancy tests prior to starting the study drug. The first pregnancy test must be performed within the 10–14 days prior to the start of study drug and the second pregnancy test must be performed within the 24 hours prior to the start of study drug. The patient must not receive study drug until the study doctor has verified that the results of these pregnancy tests are negative.

Subsequent pregnancy tests will be conducted:

- every week for the first 28 days of the study
- every 28 days thereafter (or every 14 days if the patient has irregular periods)
- if the FCBP patient misses a period
- if the FCBP patient has unusual menstrual bleeding
- at the EOT Visit
- fourteen (14) days and 28 days (if irregular periods) and 28 days only (with regular periods) after stopping LEN.

Note: Central laboratory tests will need to be performed only until Cycle 24 for each patient, as applicable.

In addition, pregnancy and risk counselling will be conducted at the time points specified in the LEN Pregnancy Risk Minimisation Plan for Clinical Trials.

7.2.13.4 PK Assessments

Concentration-time profiles and PK parameters will be assessed for MOR00208 according to the Schedule of Assessments ([Table 5](#)). Neither samples nor concentration-time profiles or PK parameters will be assessed for LEN.

Serum samples for PK analysis of MOR00208 will be handled and stored as specified in the laboratory manual at the study site until shipment on dry ice to an external analytical laboratory.

At each sampling time point, the obtained serum sample should be split into 2 aliquots (a primary and a back-up sample).

7.2.13.5 Immunogenicity

Serum samples for anti-MOR00208 antibody analysis will be collected according to the Schedule of Assessments ([Table 5](#)).

Serum samples for anti-MOR00208 antibody analysis will be handled and stored as specified in the laboratory manual at the study site until shipment on dry ice to an external analytical laboratory. At each sampling time point, the obtained serum sample should be split into 2 aliquots (a primary and a back-up sample).

7.2.13.6 Other Laboratory Evaluations

A mucosal cheek swab will be used for DNA analysis of Fc γ RIIa and Fc γ RIIIa polymorphisms. The evaluation will be performed at a specified laboratory.

Genotyping is optional; it will only be performed if the patient specifically consents to this analysis. A patient can participate in the study regardless of whether they consent to undergo genotyping.

Biomarker analysis on collected tissue samples, for example CD19 and CD 20 expression assessments will be performed at a central specified laboratory.

For evaluation of the status of the patient's immune system, B-, T- and NK cells in peripheral blood will be measured frequently throughout the study (exploratory assay). The absolute and percentage changes from baseline will be evaluated.

Baseline CD16 expression on NK cells in peripheral blood will be evaluated at baseline (exploratory assay). In addition, the ADCC capacity of the patient will be assessed.

7.2.14 Efficacy Assessments

Efficacy will be evaluated in terms of ORR, DCR, DoR, PFS, OS, TTP and TTNT: For definitions see [Section 10.6](#).

Disease response assessments will be made according to the revised response criteria based on the guidelines of the IWG reported by Cheson et al. (2007) (see [Appendix G](#)). Response assessment made by the central radiology + clinical review at Cycle 12 Day 28 (± 4 days) (and / or at the EOT visit, as applicable) will be considered for the main efficacy analysis (primary endpoint).

Local assessment of efficacy / disease response will be recorded in addition to central review at the end of Cycle 12 (for decisions concerning the additional Cycle 13 through Cycle 24 MOR00208 treatment) and at the EOT Visit (to determine whether the disease has progressed), and at additional time points specified in [Table 5](#). Disease assessment by CT/MRI during additional treatment phase will be done as follows:

- Cycle 13 until Cycle 24: First assessment during this phase can be done after approximately 3 months + 2 days after Cycle 12 D28 PET/CT assessment. Thus, this assessment is not needed at Cycle 13 Day 1, and an interval longer than 3 months is acceptable for Cycle 16 Day 1 assessment. Thereafter, it will be repeated approximately every 3 months ± 2 days from the previous scan.
- Cycle 25 onwards: approximately once every year from the previous scan.

7.2.14.1 Tumour Imaging Assessment

In the course of the study, disease and response assessments as well as tumour measurements will be performed.

Initial disease and disease response assessments for the primary endpoint will be made by positron emission tomography (PET)/ CT (CT should be done with IV contrast) at screening and Day 28 (± 4 days) of Cycle 12 and at the EOT Visit, in the cases where a patient is withdrawn from treatment before the end of Cycle 12 for reasons other than progressive disease. PET/CT scanning during additional treatment phase (Cycle 13 onwards) with MOR00208 will be performed at the decision of the investigator, and should not be performed more than approximately once per year.

Tumour measurements and disease assessment (local) will be performed as indicated in [Table 5](#) by CT. The CT portion of PET/CT will be acceptable in place of CT for tumour measurement and disease assessment, *only* when the CT portion is of adequate diagnostic-quality, and using adequate intravenous contrast.

Magnetic resonance imaging (MRI) may be used in lieu of CT, and PET/MRI in lieu of PET/CT for patients with contraindications to the administration of contrast agents, or due to other medical reasons, at the same time points as CT, or in addition to CT, at the discretion of the investigator (in this case, MRI may be performed as/when appropriate). The method used at baseline should be used throughout the study unless otherwise medically indicated.

If available and of acceptable quality, previously performed PET/CT examinations, in accordance with the standard of care, that were done up to four weeks prior to the date of informed consent may be used for a patient's baseline central radiology assessment. Additional PET/CT or CT or MRI examinations may be performed by the investigator in the course of the study, if deemed necessary (e.g., to confirm the occurrence of a CR or to make important treatmentrelated- decisions). Whenever feasible, in such cases the investigator should seek prior approval of the sponsor for the additional imaging.

If the patient discontinues from treatment, a PET/CT scan is only required at the EOT Visit if it was not performed in the cycle prior to the end of treatment. CT may be performed in lieu of PET/CT if the patient discontinues from treatment within Cycle 1.

The same scan modality should be used for all assessments, and all patients are required to have scans of the neck/chest/abdomen/pelvis. All scans conducted during the study will be provided to a central imaging laboratory for independent radiological and clinical evaluation.

If it is impossible for the patient to have their PET examination in fasted state, adequate procedures should be in place to measure and control blood glucose level.

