5.4.2 Exclusion Criteria

Exclusionary Diagnosis

1. Patients who have:
 - a) any other histological type of lymphoma including primary mediastinal (thymic) large B-cell (PMBL) or Burkitt lymphoma
 - b) primary refractory DLBCL (see [Section 5.1.1](#) for definitions)
 - c) a history of "double/triple hit" genetics DLBCL characterised by simultaneous detection of MYC with BCL-2 and/or BCL-6 translocation(s) defined by fluorescence *in situ* hybridisation. MYC, BCL-2, BCL-6 testing prior to study enrolment is not required

Exclusionary Previous and Current Treatment

2. Patients who have, within the 14 days prior to Day 1 dosing:
 - a) not discontinued CD20-targeted therapy, chemotherapy, radiotherapy, investigational anticancer therapy or other lymphomaspecific- therapy
 - b) undergone major surgery or suffered from significant traumatic injury
 - c) received live vaccines (see [Section 6.7](#) for details)
 - d) required parenteral antimicrobial therapy for active, intercurrent infections
3. Patients who:
 - a) have, in the opinion of the investigator, not recovered sufficiently from the adverse toxic effects of prior therapies
 - b) were previously treated with CD19-targeted therapy or IMiDs® (e.g., thalidomide, LEN)
 - c) have a history of hypersensitivity to compounds of similar biological or chemical composition to MOR00208, IMiDs® and/or the excipients contained in the study drug formulations
 - d) have undergone ASCT within the period ≤ 3 months prior to the signing of the informed consent form. Patients who have a more distant history of ASCT must exhibit full haematological recovery before enrolment into the study
 - e) have undergone previous allogenic stem cell transplantation
 - f) have a history of deep venous thrombosis/embolism, threatening thromboembolism or known thrombophilia or are at a high risk for a thromboembolic event in the opinion of the investigator and who are not willing/able to take venous thromboembolic event prophylaxis during the entire treatment period
 - g) concurrently use other anticancer or experimental treatments

Exclusionary Patient's Medical History

4. Prior history of malignancies other than DLBCL, unless the patient has been free of the disease for ≥ 5 years prior to screening. Exceptions to the ≥ 5 year time limit include history of the following:
 - a) basal cell carcinoma of the skin
 - b) squamous cell carcinoma of the skin
 - c) carcinoma *in situ* of the cervix
 - d) carcinoma *in situ* of the breast

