Patients should not have received a CD20-targeted therapy, chemotherapy, radiotherapy, investigational anticancer therapy or other lymphomaspecific- therapy within 14 days prior to Cycle 1 day 1 of the study. In addition, no radiotherapy (including limited field radiotherapy) is permitted after the baseline PET/CT scan for initial disease assessment has been performed. Other than the study drugs, patients should not receive any other DLBCLspecific- therapy during the study treatment period. The patient should not receive any investigational agent other than MOR00208 and LEN during the treatment period of the study.

The use of concurrent antineoplastic therapies other than study drugs, including, but not limited to, chemotherapies, hormonal therapy, immunotherapy, biological response modifiers, mAbs with or without conjugation, radioisotopic therapies, stem cell transplant and targeted small molecules are not permitted during the entire treatment period (i.e., prior to disease progression during this study) of this study. After disease progression has been recorded, additional antineoplastic therapies are permitted at the discretion of the investigator and in accordance with the local guidelines and should be recorded in the eCRF.

Systemic Glucocorticosteroids

The use of systemic glucocorticosteroids is generally discouraged because their potential antilymphoma activity in patients with DLBCL may confound interpretation of antitumor effects mediated by study drug treatment (MOR00208 and LEN).

However systemic corticosteroids in doses up to 20 mg/day prednisone or equivalent (i.e. equipotent corticosteroid) are permitted, provided the dosing is stable (not increased within the last month), but only for the treatment of non-neoplastic comorbid indications (e.g. rheumatoid arthritis).

-Screening:

Patients may potentially receive systemic glucocorticosteroids in doses above 20 mg/day (prednisone or equivalent) to manage severe DLBCL manifestations (e.g., compressive disease, rapidly progressing symptomatic adenopathy) during Screening as per institutional standards. For these patients the glucocorticosteroids treatment needs to be tapered to a total daily dosage of 20 mg or less of prednisone or its equivalent prior to study drug(s) administration on Cycle 1, Day 1.

-Cycle 1 through EOT visit:

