7.2.1 Screening followed by Enrolment (Start of IMP)

The Screening Period begins on the date the Informed Consent Form (ICF) is signed and will last for up to 28 days. The ICF must be signed prior to beginning any assessments solely for the purpose of this study. Standard of care assessments done on the day of consent (but prior to signing the ICF) do not need to be repeated solely for the purpose of screening and may be used as study data, if they meet the protocol requirements.

During screening, it is permitted to repeat on a **single occasion** the **central laboratory assessment** of serum chemistry and haematology parameters due to the variability of the parameters and their dependence on multitude of factors (e.g., hydration, muscle mass). This is, provided no safety concerns arise and that such laboratory results might have been caused by a transient, medically plausible event, which resolved spontaneously or as result of a medical intervention in the meantime (e.g., dehydration, vomiting, imaging procedure with a contrast). This procedure and the rationale behind it must be explicitly documented in source data. Such repeated assessment (once only) of the concerned parameters will not be counted as “re-screening” for that patient.

On Cycle 1 Day 1, patient eligibility must be confirmed before drug administration. Local laboratory parameters should be used for this purpose, as specified in [Section 7.2.13](#) Laboratory Assessments.

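### The baseline PET/CT can be 56 days old at first dose, and lymphoma-directed steroids (less so other systemic therapy) may follow it with no re-scan, so their shrinkage could count towards the primary ORR

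*Protocol*

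**What the plan says.** **Age of the scan.** Protocol 7.2.14.1 says that earlier standard-of-care PET/CT examinations "that were done up to four weeks prior to the date of informed consent may be used" as the baseline for central review. Protocol 7.2.1 starts screening at consent and says it "will last for up to 28 days".

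**What may follow the scan.** Protocol 6.7 protects the baseline from one modality: "no radiotherapy (including limited field radiotherapy) is permitted after the baseline PET/CT scan for initial disease assessment has been performed". Chemotherapy, CD20-targeted, investigational and other lymphoma therapy is tied to first dose, not to the scan. Exclusion criterion 2 in Protocol 5.4.2 opens with "Patients who have, within the 14 days prior to Day 1 dosing", and 6.7 repeats the 14 days. On steroids, 6.7 says of the screening period: "Patients may potentially receive systemic glucocorticosteroids in doses above 20 mg/day (prednisone or equivalent) to manage severe DLBCL manifestations". The condition attached is a taper to 20 mg/day or less before Cycle 1 Day 1, not a new scan. The same section discourages systemic steroids because "their potential antilymphoma activity in patients with DLBCL may confound interpretation of antitumor effects".

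**Contrast with bone marrow.** Protocol 7.2.14.2 also accepts a marrow result from the four weeks before consent, but only where disease has stayed stable in between. The PET/CT rule has no such condition.

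**Analysis.** SAP 6.7 takes as efficacy baseline the latest available assessment up to the start of treatment, but describes the baseline period as starting at consent. SAP 9.1 counts a best response of CR or PR at any time. The ORR sensitivity analyses in SAP 9.3 do not use scan age or therapy given after the scan.

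**The concern.** PR requires the sum of the products of the diameters (SPD) to fall by at least half (Protocol Appendix G). If the reference scan precedes a course of treatment that shrinks the tumour, part of that fall was not produced by the study drugs. A single-arm trial has no control group in which the same carry-over would appear, so it cannot be separated from the effect of the combination. The patients most exposed are those given steroids in screening for compressive or fast-growing disease.

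The protocol recognises both halves of the problem: it bars radiotherapy after the baseline scan, and it names steroids as a confounder of response. It does not join the two for PET/CT. The per-protocol analysis does not help, because a patient handled this way is compliant.

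**Working it through.** **1. The plan's own figures.** The documents give no maximum scan age; it follows from two windows (step 2). They do give an ORR benchmark (Protocol 10.8, SAP 5.3): 20% against 35%, two-sided 5%, power 85%, 73 patients, with an observed 32% called significant.

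- N = ((1.960 × √(0.20 × 0.80) + 1.036 × √(0.35 × 0.65)) / 0.15)² = 72.6, so 73. Reproduced by the normal approximation.
- Smallest count whose exact upper tail under 20% is at most 2.5%: 23 of 73 = 31.5%, which matches the stated 32%. At 80 patients it is 24 (30.0%), with an upper tail of 2.17%.

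**2. Timeline.**

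- Maximum scan age at Cycle 1 Day 1: 28 days before consent + 28 days of screening = 56 days.
- Part of that interval open to systemic lymphoma therapy: 56 − 14 = 42 days.
- Part expressly open to lymphoma-directed steroids above 20 mg/day: the 28-day screening period.
- First scheduled on-study scan: Cycle 3 Day 1 (Protocol Table 5, SAP Table 12), 2 × 28 = 56 days after first dose.

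**3. Effect on the PR threshold.** If SPD has already fallen by a fraction s since the scan, the further on-study fall needed for PR is 1 − 0.5/(1 − s). If it has grown by g, the fall needed is 1 − 0.5/(1 + g).

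| Change in SPD from scan to first dose | On-study fall needed for PR |
|---|---|
| none | 50% |
| 20% fall | 37.5% |
| 30% fall | 28.6% |
| 40% fall | 16.7% |
| 25% growth | 60% |

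The bias can go either way. CR by PET negativity depends less on baseline size, although earlier therapy can still contribute to it.

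**4. Illustration of consequence.** One response at 80 patients is 1/80 = 1.25 points. The number of carry-over responders, k, is an assumption; the documents give none. With a true ORR of 20%, the chance of reaching the benchmark is P(X ≥ 24), where X is binomial with n = 80 and p = 0.20 + k/80:

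| k (assumed) | p | P(X ≥ 24) |
|---|---|---|
| 0 | 0.2000 | 2.2% |
| 1 | 0.2125 | 4.2% |
| 2 | 0.2250 | 7.4% |
| 4 | 0.2500 | 18.2% |
| 8 | 0.3000 | 54.2% |

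This takes each of the k as a patient turned from non-responder to responder, with no offset from growth. It shows sensitivity and is not an estimate. The plan intends no formal test; 24 of 80 serves only as the counterpart of its benchmark.

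**5. Can affected patients be identified?** Protocol 6.7 records medications from 30 days before consent, which covers the 28-day pre-consent allowance. Protocol 7.2.7 records start and stop dates of prior therapy. The dates needed are therefore already collected.

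**The case against.** Several points against are sound.

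- **Eligibility narrows the chemotherapy and CD20 route.** Treatment given after an old scan becomes the latest systemic therapy. Under inclusion 4a and Protocol 5.1.1 the patient must then have fallen short of PR on it or relapsed after it, so mainly shrinkage below PR can carry over. The route is not closed, because Protocol 7.2.7 lists imaging only as one example of evidence for the latest progression. The steroid route has no comparable check.
- **A later scan replaces the old one.** Under SAP 6.7 any pre-dose re-scan becomes baseline. The gap is confined to patients treated after their scan and not re-imaged.
- **Growth offsets carry-over.** Rapidly progressing patients may also have grown since the scan, so the net sign is unknown.
- **Persistence.** Carry-over must still be visible at Cycle 3 Day 1, 56 days after first dose. This weakens any claim that responses would look earlier.
- **The exposure is not hidden.** Prior and concomitant medications are summarised and listed (SAP 8.7.3), and time since the last anti-DLBCL treatment is listed per patient (SAP 20.2). What is missing is the link to the scan date.
- **The independent review charter** may contain a rule for choosing the baseline scan. It is not among these documents.

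One reassurance does not carry over. The statement in Protocol 6.7 that short courses above 20 mg/day are unlikely to confound concerns flares of non-neoplastic conditions from Cycle 1 onward, not lymphoma treatment in screening.

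**Conclusion.** The gap in the text is real. The scan used as baseline can be 56 days old, only radiotherapy is barred after it, and neither document requires a re-scan after lymphoma-directed steroids or other lymphoma therapy. Shrinkage from such treatment could be credited to the combination in the primary ORR, mainly through steroids in screening and secondarily through systemic therapy that achieved less than PR.

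Three stronger readings are tempting and not supported:

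- A reader might infer that chemotherapy or CD20 antibody responses pass freely into the ORR. Eligibility prevents most of that.
- A reader might infer that ORR and CR rate are inflated by a known amount, for example 2 to 6 patients, or 2.5 to 7.5 points against the planned 15. No document gives a count, not every exposed patient would change category, and growth since an old scan works the other way.
- A reader might infer that these patients cannot be traced. The data are collected but not linked to the scan.

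The conclusion rests on the two windows being additive, as written, and on the review charter not already setting a stricter rule. It is worth correcting because the correction is small, not because a bias of known size has been shown.

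**What to change.** 1. **Protocol 7.2.14.1.** Accept a pre-consent PET/CT as central baseline only if no lymphoma-directed therapy, including steroids above 20 mg/day given for lymphoma, was given after it; otherwise the screening PET/CT already scheduled for every patient is done. This parallels the marrow condition in 7.2.14.2. Leave all treatment allowances unchanged. Reconcile the pre-consent allowance with SAP 6.7, whose baseline period starts at consent.
2. **SAP 9.3.** Add an ORR analysis (central review, FAS) that counts as non-responders the patients who received such therapy between baseline scan and first dose, labelled as a conservative lower bound. Report how many there are, and the distribution of the interval from scan to Cycle 1 Day 1.

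The second item also covers patients scanned early in screening and then given steroids, whom the first does not reach. Requiring every scan to follow the last steroid dose would close that remainder too, but could delay treatment in urgent patients; that trade-off is not part of this proposal.

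**Cost.** A few old scans could not be reused. The sensitivity ORR may be slightly lower than the main result because it discards some genuine responses. The SAP item needs no new data and remains possible if enrolment has finished.
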